724 *Determined by masked grader at the central reading center.

725 To ensure that statistical outliers do not have undue impact on analyses of continuous outcomes,
726 change in continuous outcomes from baseline will be truncated to ± 3 standard deviations based
727 on the overall mean and standard deviation from both treatment groups combined at 24 weeks.

728 **8.5 Analysis Cohorts**

729 • Intention-To-Treat (ITT) Analysis Cohort: all randomized participants irrespective of
730 treatment received, and analyzed according to treatment assignment.

731 • Safety Analysis Cohort: all randomized participants irrespective of treatment received,
732 and analyzed according to treatment assignment.

733 • Per-Protocol Analysis Cohort: only participants that complete the initial treatment (PVL
734 or sham injection) and do not receive any non-protocol treatments during follow-up.
735 Vitrectomy performed according to the criteria in section 4.2.1 is considered per-protocol
736 and will be included in this analysis.

737 The primary analysis will follow the ITT principle. It will include all randomized participants.
738 The data from the ITT cohort will be analyzed according to the group to which the participants
739 were assigned through randomization, regardless of treatment actually received.

740 A per-protocol analysis will be performed to provide additional information regarding the
741 magnitude of the treatment effect. The per-protocol analysis will only be performed if more than
742 10% of randomized participants would be excluded by these criteria (e.g., 13 or more
743 participants if exactly 124 are enrolled).

744 The ITT analysis is considered the primary analysis. If the results of the per-protocol and ITT
745 analyses give inconsistent results, the per-protocol analysis will be interpreted with caution. In
746 this scenario, exploratory analyses will be performed to evaluate possible factors contributing to
747 the differences.

748 **8.6 Analysis of the Primary Efficacy Outcome**

749 The primary outcome of central VMT release without rescue treatment at 24 weeks is a binary
750 variable that is graded by the central reading center. Logistic regression with robust variance
751 estimation will be used to test the hypothesis of superiority (Section 8.2). Presence of ERM
752 within 1 mm of the center of the macula at baseline will be included as a covariate, as previous

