65 The data from the ITT cohort will be analyzed according to the group to which the participants
66 were assigned through randomization, regardless of treatment actually received.

67 A per-protocol analysis will be performed to provide additional information regarding the
68 magnitude of the treatment effect. The per-protocol analysis will only be performed if more than
69 10% of randomized participants would be excluded by these criteria (e.g., 13 or more
70 participants if exactly 124 are enrolled).

71 The ITT analysis is considered the primary analysis. If the results of the per-protocol and ITT
72 analyses give inconsistent results, then the per-protocol analysis will be interpreted with caution.
73 In this scenario, exploratory analyses will be performed to evaluate possible factors contributing
74 to the differences.

75 **1.4 Analysis of the Primary Efficacy Outcome**

76 The primary outcome of central VMT release without rescue treatment at 24 weeks is a binary
77 variable that is graded by the central reading center. Logistic regression will be used to test the
78 hypothesis of superiority. The risk difference for the treatment group effect (estimated with
79 conditional standardization)⁴, along with the 95% confidence interval (estimated with the delta
80 method)⁴ and *P* value will be used to compare treatment groups. To aid in interpretation of the
81 risk difference, observed outcome proportions will be reported for each treatment group.

82 Since the chance of re-attachment after release before 24 weeks is highly unlikely, an eye with
83 central VMT release without rescue treatment prior to 24 weeks will be considered to have met
84 the outcome through 24 weeks if the participant is lost to follow-up. Similarly, any eye receiving
85 rescue treatment prior to 24 weeks will be considered not to have met the outcome through 24
86 weeks.

87 Multiple imputation will be used to impute missing data for eyes lost to follow-up that did not
88 have prior release or rescue treatment documented. The imputation model will treatment group,
89 and VMT status at 1, 4, 12, and 24 weeks.

90 A sensitivity analysis will be conducted using the same approach as above, but without multiple
91 imputation (i.e., complete-case analysis).

92 **1.5 Analysis of the Secondary and Exploratory Efficacy Outcomes**

93 The ITT analysis cohort will be used for all secondary and exploratory outcomes.

94 **1.5.1 Secondary Efficacy Outcomes**

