195 Secondary subgroup analyses will include ERM presence at the site of vitreous adhesion, lens
196 status (phakic or pseudophakic), retinoschisis, subretinal fluid within the central 1 mm, length of
197 adhesion on OCT (less than or equal to 1500 microns or greater than 1500 microns), and diabetes
198 status (has diabetes or does not have diabetes). Subgroups will be defined by the value at
199 baseline.

200 There are no data to suggest that the treatment effect will vary by sex or race/ethnicity. However,
201 both of these factors will be evaluated in exploratory subgroup analyses as mandated by National
202 Institutes of Health (NIH) guidelines.

203 Subgroup factors will be analyzed as categorical and continuous or ordinal variables where
204 possible. Secondary and exploratory subgroup analyses will only be conducted if there are at
205 least 20 eyes in each subgroup for each treatment group. The primary subgroup analysis will be
206 conducted regardless of sample size.

207 **1.12 Multiple Testing**

208 There will be no formal adjustment for multiple testing. Only $P \leq .05$ will be considered of
209 interest.

210 **1.13 Visit Windows for Analysis**

211 The analysis windows for visits will be defined according to Table 1. If multiple visits fall within
212 the same window, priority will be given to the protocol visit over unspecified visits. If there is no
213 protocol visit in the window, then the visit closest to the target date (but within the analysis
214 window) will be designated as the analysis visit. Visit windows will be filled in the following
215 order to handle visits occurring on the border of two windows: 24 weeks, 12 weeks, 4 weeks, 1
216 week.

217 **Table 1. Analysis Windows**

Visit \pm Protocol Window	Target	Analysis Window
1 week (-4 days to +3 days)	7 days	1 day – 2 weeks (1 – 14 days)
4 (± 1) weeks	28 days	2 – 8 weeks (14 – 56 days)
12 (± 2) weeks	84 days	8 – 18 weeks (56 – 126 days)
24 (± 4) weeks	168 days	18 – 40 weeks (126 – 280 days)

218 **1.14 Missing Data**

219 The strategy for handling missing data generally is included with the description of each
220 analysis. For analyses using multiple imputation, the Markov chain Monte Carlo (MCMC)
221 method with 100 imputations will be used. Where otherwise not specified, only participants with
222 non-missing data are included in analyses (i.e., complete-case analysis).

223 **1.15 Outliers**

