224 To ensure that statistical outliers do not have an undue impact on analyses of continuous
225 outcomes, change in continuous outcomes from baseline will be truncated to ± 3 standard
226 deviations based on the overall mean and standard deviation from both treatment groups
227 combined at 24 weeks. Truncation will occur after imputation, where applicable.

228 **1.16 Model Assumptions and Nonconvergence**

229 All model assumptions will be verified. If model assumptions are seriously violated, covariates
230 may be categorized or excluded, and a non-parametric approach, robust method, or
231 transformation may be considered. The proportional hazards assumption will be assessed by
232 visual inspection of Kaplan-Meier curves. If the proportional hazards assumption is seriously
233 violated, then an alternative approach, such as analysis of restricted mean survival time, may be
234 undertaken.

235 If a logistic regression models fail to converge, then covariates will be excluded, missing data
236 will not be imputed (where applicable), the confidence interval for the risk difference will be
237 estimated with the Newcombe method, and the *P* value for the treatment group comparison will
238 be calculated with Barnard's unconditional exact test.

239 **1.17 Revisions**

240 Owing to lower than anticipated final sample size, the following key changes were made to the
241 analysis plan after review of study data:

- 242 • Presence of epiretinal membrane has been removed as a covariate from all imputation
243 and regression models.
- 244 • Proportion of eyes with central VMT release and vitreopapillary traction (VPT) release
245 without rescue treatment at 24 weeks has been removed from the list of secondary
246 outcomes.
- 247 • A sensitivity analysis of confounding for the primary outcome has been removed.
- 248 • An alternative analysis method has been described for outcomes in which logistic
249 regression fails to converge.

250 In addition, treatment and subgroup effects from all logistic regression analyses will now be
251 summarized with a risk difference instead of a relative risk.

252 **References**

253 1. Dugel PU, Tolentino M, Feiner L, Kozma P, Leroy A. Results of the 2-Year Ocriplasmin
254 for Treatment for Symptomatic Vitreomacular Adhesion Including Macular Hole
255 (OASIS) Randomized Trial. *Ophthalmology*. 2016;123(10):2232-2247.

256 2. Stalmans P, Benz MS, Gandorfer A, et al. Enzymatic vitreolysis with ocriplasmin for

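### Does SAP 1.4 need to name the test behind the primary P value?

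*SAP*

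**What the plan says.** SAP 1.4 gives the model in one sentence ("Logistic regression will be used to test the" superiority hypothesis). The next sentence gives the estimate: a risk difference by conditional standardization, "along with the 95% confidence interval (estimated with the delta" method, and a P value. It says that the "value will be used to compare treatment groups. To aid in interpretation of the" risk difference, observed proportions are also reported. The estimate and the interval each have a named method. The P value has none.

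Other parts of the plan bear on this:

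- **SAP 1.12** sets the threshold: "Only $P \leq .05$ will be considered of" interest.
- **SAP 1.14** states that the MCMC "method with 100 imputations will be used".
- **SAP 1.16** names both methods for a logistic model that fails to converge: the interval is "estimated with the Newcombe method" and the P value comes from Barnard's test.
- **SAP 1.17** records that "Presence of epiretinal membrane has been removed as a covariate from all imputation" and regression models. Treatment is then the only term in the primary model.
- **Protocol 8.6** has "Logistic regression with robust variance" estimation. SAP 1.4 does not repeat the robust variance, and SAP 1.17 does not list its removal.

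**The concern.** The fallback analysis has a named test and the main analysis does not. The threshold applies to the P value, while the effect is reported through an interval on another scale. A test of the log odds ratio and a delta-method interval for the risk difference do not always agree, so a report could show P above .05 beside an interval that excludes zero. Neither SAP 1.4 nor SAP 1.12 says which one then decides.

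Timing adds to this. The SAP version table says that version 2.0 followed early stopping and a review of study data. A statistic left open at that point could be chosen with the results known. The robust-variance wording also disappeared without an entry in SAP 1.17, which could suggest that the test itself had changed. What is at stake is whether a borderline primary result is called significant.

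**Working it through.** **Inputs.** Allocation is 1:1 (Protocol summary). The threshold is P ≤ .05 (SAP 1.12). The design rates are 60% v 30% (Protocol 8.3.2). Protocol 8.3.1 cites sham release at 6 months of about 13% and 10%, and gas release of 60% in one series and 80% among eyes with VMT only in another. The reduced final sample size is not given, so two ranges per arm are assumed: 15-30 and 31-61. Arms are taken as equal and all outcomes as observed.

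**The plan's own figure.** With pooled variance and no continuity correction, n per group = [1.960 × √(2 × 0.45 × 0.55) + 1.282 × √(0.6 × 0.4 + 0.3 × 0.7)]² / 0.3² = 55.7, so 56 per group and 112 in total. This matches Table 1 of Protocol 8.3.2, and nothing here affects it.

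**Candidate tests.** With a of n releases v b of n, and treatment as the only term:

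- Wald: z = ln[a(n−b) / (b(n−a))] / √[1/a + 1/(n−a) + 1/b + 1/(n−b)].
- Likelihood ratio: twice the log-likelihood gain over a common rate, referred to chi-square with 1 degree of freedom.
- Risk-difference z: (p₁−p₂) / √[p₁(1−p₁)/n + p₂(1−p₂)/n]. This is the standard error of the delta-method interval, so with no imputed outcomes this test always agrees with the interval.

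**Example, 12/19 v 6/19.** The log odds ratio is 1.312 with SE 0.685, so z = 1.91 and Wald P = .056. The likelihood-ratio chi-square is 3.87, P = .049. The risk difference is 0.316 with SE 0.154, so z = 2.05, P = .040, and the interval is 1.5 to 61.7 points.

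**Example, 12/20 v 6/20.** Wald P = .061, likelihood-ratio P = .054 and risk-difference P = .0455. The interval is 0.6 to 59.4 points.

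**How often it happens.** Every 2×2 table was enumerated at each n and weighted by its binomial probability. Tables with an empty or full cell go to the SAP 1.16 fallback. The figures are mean shares of trials over each range of n.

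| True rates | Interval excludes 0, Wald P > .05 (15-30 / 31-61) | Wald and likelihood ratio on opposite sides of .05 (15-30 / 31-61) |
|---|---|---|
| 60% v 30% | 4.3% / 1.6% | 2.0% / 0.7% |
| 60% v 13% | 2.4% / 0.1% | 1.5% / <0.1% |
| 80% v 10% | <0.1% / ~0% | <0.1% / ~0% |

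The shares jump with n because the tables are discrete. At 60% v 30% the first column is 0.2% at n=18, 12.6% at n=20 and 0.3% at n=24. At the planned 56 per group it is 0.5%.

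**Size under the null.** At common rates of 10%, 20%, 30%, 40% and 50%, averaged over n=15-30, rejection is 3.5-4.8% for Wald (largest at any n 6.5%), 4.3-5.6% for likelihood ratio (largest 7.3%) and 4.3-6.3% for the risk-difference z (largest 8.1%).

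**Robust variance.** In a model with one binary term, the squared residuals in an arm sum to n·p(1−p), which is that arm's information. The sandwich and model-based standard errors are therefore equal. At 12/20 v 6/20 both are 0.668, with P = .061 either way.

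**The case for a change.** The best case for an edit is that it costs one sentence. The authors name a test for the safety comparisons and for non-convergence, so naming one for the primary analysis would be consistent. In a trial stopped early, with a plan revised after data review, a written rule for P against the interval would forestall any question. The Wald test would suit: it fits the logistic wording and the protocol's robust variance, and it pools directly over the 100 imputations.

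The observation stands: SAP 1.4 attaches no method to the P value. The remedy achieves less than it seems to. Naming the Wald test while keeping the delta-method interval retains the very pairing that disagrees, so the first column of the table would not change. Only a P value from the same risk-difference standard error removes the mismatch. SAP 1.4 already allows that reading, since it lists the risk difference, its interval and the P value together, and SAP 1.1 states the null as a difference in proportions. That test is also the most liberal of the three, so choosing it is a trade-off and not a clear gain. Nor would the edit restore prespecification, because a test named now is also named after data review. The initial SAP is not among the documents, so whether this wording changed cannot be told. The robust-variance omission changes no number in the primary model, and SAP 1.17 sets out to list key changes only.

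**Conclusion.** No change to the plan follows. SAP 1.4 leaves a detail open that an analyst fills with a standard test of a named model, and each candidate keeps its size reasonably near 5%. The choice matters only in borderline results. At 60% v 30% with 15-30 eyes per arm, about 4% of trials on average would show an interval excluding zero beside Wald P above .05, and about 2% would have Wald and likelihood ratio on opposite sides of .05. These shares fall to 1.6% and 0.7% at 31-61 per arm, and below 0.1% at 80% v 10%. At single sample sizes they can be higher, up to 12.6% at n=20 for the first and 10.0% at n=19 for the second.

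The figures rest on assumed sample sizes, equal arms and fully observed outcomes; multiple imputation was not simulated. A reader of the results can judge a borderline case from the observed proportions, which SAP 1.4 requires for each group and from which all three tests can be recomputed when no outcomes are imputed.

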295 (including protocol refraction) in each eye (*within prior 8 days*)

- 296 4. Visual function testing (myVisionTrack) (*within prior 8 days*)
 - 297 ➤ Visual function testing will be performed using the myVisionTrack application on an
298 iPad or tablet. myVisionTrack® is an FDA cleared application to track disease
299 progression in patients with certain retinal diseases. During the test, the patient will
300 select the circle that is shaped differently among a series of side-by-side circles on the
301 screen. The series continues with increasing difficulty until the patient's visual
302 function is determined. Visual function is measured using the shape discrimination
303 hyperacuity (SDH) (logMAR) score.

- 304 5. Spectral-Domain OCT using Zeiss Cirrus or Heidelberg Spectralis on each eye (*within prior
305 8 days*)

306 ➤ OCT scans of the study eye will be promptly sent to the central reading center for
307 grading and a participant cannot be randomized until reading center confirmation of
308 eligibility has been received

309 6. Ocular examination on each eye including slit lamp, measurement of IOP, lens assessment,
310 and dilated ophthalmoscopy (*within prior 8 days*)
311 ➤ Scleral depression to rule out any retinal tears pre-operatively will be required for the
312 baseline eye exam to confirm eligibility

313 **2.4 Randomization of Eligible Participants**

314 Randomization may occur on the same day as baseline testing if eligibility is confirmed by the
315 reading center on the day of screening.

316 1. Prior to randomization, the participant's understanding of the trial, willingness to accept the
317 assigned treatment group, and commitment to the follow-up schedule should be reconfirmed.
318 2. The baseline injection (or sham) must be given on the day of randomization; therefore, a
319 participant should not be randomized until this is possible.
320 3. Randomization is completed on the DRCR Retina Network website.
321 • Study eyes will be randomly assigned with equal probability to one of two treatment
322 groups:
323 ○ Group A: PVL (Intravitreous injection of 0.3 mL C₃F₈ gas)
324 ○ Group B: Observation (Sham injection)

325 Randomization will be stratified by clinical site and presence of epiretinal membrane (ERM)
326 within 1 mm of the center of the macula, determined by Reading Center grading. Previous
327 reports have suggested that the proportions of eyes with VMT release differ depending on the
328 presence of ERM.

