654 The analysis plan synopsis in this chapter contains the framework of the anticipated final
655 analysis plan.

656 **8.2 Statistical Hypotheses**

657 A test of superiority will be used in evaluating the following hypotheses for the primary
658 outcome:

659 Null Hypothesis (H₀): There is no difference in the proportion of eyes with central VMT release
660 without rescue treatment between the PVL and observation groups at 24 weeks.

661 Alternative Hypothesis (H_a): There is a difference in the proportion of eyes with central VMT
662 release without rescue treatment between the PVL and observation groups at 24 weeks.

663 Similar hypothesis tests will be conducted for all secondary, exploratory, and safety outcomes.

664 **8.3 Sample Size**

665 **8.3.1 Outcome Projections:**

666 *Observation Group (sham injection)*

667 In a consecutive case series of 106 eyes with a median follow-up time of 18 months,⁶ the
668 proportion of eyes with spontaneous VMT release was 32%. The proportion of eyes with VMT
669 release at 6 months in the Sham Groups of the randomized controlled trials MIVI-TRUST¹⁰
670 (N = 188) and OASIS (N = 74),¹¹ which compared ocriplasmin versus sham for VMT, were
671 approximately 13% and 10%, respectively. Dugel et al.¹¹ also found that the proportion of eyes
672 with VMT release was greater among eyes that had MH at baseline. Macular hole was present at
673 baseline in approximately 36% of the OASIS Sham Group and 25% of the MIVI-TRUST Sham
674 Group.

675 *PVL group*

676 Three case series provide estimates of VMT release with C₃F₈ gas. A study of 15 eyes (1 with
677 MH) from Rodrigues et al.²³ showed release of VMT in 60% of eyes through 6 months. Steinle
678 et al.²⁴ showed 83% success among 30 eyes (3 with MH) through 62 days. Finally, Chan et al.²⁵
679 (2017) showed 86% success among 50 eyes (15 with MH) over 9 weeks. In addition, Chan et al.
680 reported higher rates of VMT release among eyes with MH. The release rate among eyes with
681 VMT only in Chan et al. was 80%.²⁵

682 **8.3.2 Sample Size Estimates**

683 Table 1 shows sample size estimates for the primary analysis under varying assumptions for the
684 proportion of eyes with VMT release within the 2 groups. These calculations assume a Type I
685 error rate of 5%, 90% power, and a two-sided test of superiority (See Section 8.6) with a null
686 hypothesis of no difference between the groups (Section 8.2).

687

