Table 1: Comparison of Proportion with VMT Release: Total Sample Size

Release in PVL Group	Release in Sham Group		
	10%	20%	30%
50%	52	104	248
60%	34	60	112
70%	24	38	62

688 For true outcome proportion of 60% (PVL) vs 30% (sham injection), a sample size of 112 (56
 689 per group) gives 90% power to reject the null hypothesis of no difference. Adjusting for possible
 690 loss to follow-up of 10% gives a final sample size of 124 (62 per group).

691 **8.4 Outcome Measures**

692 *For the outcomes below, rescue treatment includes vitrectomy, ocriplasmin, or additional
 693 pneumatic vitreolysis during the course of the study.*

694 Primary Efficacy Outcome:

- 695 • Proportion of eyes with central VMT release* without rescue treatment at 24 weeks.
 - 696 ○ For purposes of description only, the distribution of eyes within treatment group
 697 by the following categories at 24 weeks will be tabulated without statistical
 698 comparison:
 - 699 ▪ Central VMT release without rescue treatment
 - 700 ▪ Central VMT release with rescue treatment
 - 701 ▪ No central VMT release and no rescue treatment
 - 702 ▪ No central VMT release despite rescue treatment

703 Secondary Efficacy Outcomes:

- 704 • Proportion of eyes with central VMT release* without rescue treatment through 24 weeks
 705 (time-to-event analysis).
- 706 • Proportion of eyes with central VMT release and vitreopapillary traction release* without
 707 rescue treatment at 24 weeks.
- 708 • Mean change in visual acuity letter score from baseline at 24 weeks.
- 709 • Proportion of eyes with at least 10-letter gain (increase) in visual acuity from baseline at
 710 24 weeks.
- 711 • Proportion of eyes with at least 10-letter loss (decrease) in visual acuity from baseline at
 712 24 weeks.
- 713 • Proportion of eyes receiving rescue treatment before the 24-week visit.
 - 714 ○ For purposes of description only, the following will be tabulated within treatment
 715 group without statistical comparison:
 - 716 ▪ Proportion of eyes receiving rescue treatment before the 24-week visit or
 717 for which rescue treatment is planned at the 24-week visit and medical
 718 records confirm rescue treatment occurred within the subsequent 12
 719 weeks.

720 ■ Type of rescue treatment.

721 Exploratory Efficacy Outcomes:

722 • Mean change in shape discrimination hyperacuity from baseline at 24 weeks.

723 • Proportion of eyes with ellipsoid zone* integrity at 24 weeks.

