753 reports have indicated the rate of VMT release differs by presence of ERM and the
754 randomization schedules were therefore stratified by presence of ERM. The relative risk
755 (estimated using the method of Localio et al. 2007²⁷) for the treatment group effect, 95%
756 confidence interval, and *P* value will be used to compare treatment groups. To aid in interpretation
757 of the relative risk, observed outcome proportions will be reported for each treatment group.

758 Since the chance of re-attachment after release is highly unlikely before 24 weeks, an eye with
759 central VMT release without rescue treatment prior to 24 weeks will be considered to have met

760 the outcome through 24 weeks if the patient is lost to follow-up. Similarly, any eye receiving
761 rescue treatment prior to 24 weeks will be considered not to have met the outcome through 24
762 weeks because rescue treatment will have been given.

763 Multiple imputation will be used to impute missing data for eyes lost to follow-up that did not
764 have prior release or rescue treatment documented. The imputation model will include presence
765 of ERM within 1 mm of the center of the macula at baseline, treatment group, and VMT status at
766 1, 4, 12, and 24 weeks.

767 A sensitivity analysis will be conducted using the same approach as above but without multiple
768 imputation (i.e., complete-case analysis).

769 **8.7 Analysis of the Secondary and Exploratory Efficacy Outcomes**

770 The ITT analysis cohort will be used for all secondary and exploratory outcomes.

771 **8.7.1. Secondary Efficacy Outcomes**

772 Development of central VMT release without rescue treatment through 24 weeks is a time-to-
773 event outcome that will be modeled with Cox proportional hazards regression and robust
774 variance estimation. The hazard ratio along with the 95% confidence interval and *P* value will be
775 used to compare treatment groups. To aid in interpretation, a Kaplan-Meier plot will be
776 constructed. Data from eyes not observed to have release or that receive rescue treatment will be
777 censored on the date of their final visit.

778 The proportion of eyes with central VMT release and vitreopapillary traction release (without
779 rescue treatment) at 24 weeks is a binary variable graded by the central reading center that will
780 be analyzed with logistic regression. Analysis and imputation of missing data will be handled in

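### Complete-case is the only sensitivity analysis for missing primary outcomes, and comparing it with the imputed result does not test whether loss depends on the unseen 24-week outcome

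*SAP*

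**What the plan says.** SAP 1.4 settles some lost eyes by rule. An eye with "central VMT release without rescue treatment prior to 24 weeks will be considered to have met" the outcome if the participant is then lost, and an eye with "rescue treatment prior to 24 weeks will be considered not to have met the outcome through 24" weeks. Eyes lost with neither event documented are multiply imputed from treatment group and VMT status at 1, 4, 12 and 24 weeks. SAP 1.17 records that ERM was taken out of all imputation models.

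The check on this is one sentence: "A sensitivity analysis will be conducted using the same approach as above, but without multiple" imputation, glossed as complete-case. Protocol 8.6 has the same sentence: "A sensitivity analysis will be conducted using the same approach as above but without multiple" imputation. SAP 1.11 describes the complete-case set as eyes that finish the 24-week visit or that had release or rescue before it.

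Neither document has a tipping-point, delta-adjusted, best/worst-case or missing-equals-failure analysis. The per-protocol analysis (SAP 1.3) is about treatment received. The confounding analysis of Protocol 8.15 used observed data and was dropped in SAP 1.17. The Cox analysis (SAP 1.5.1) censors unreleased eyes at their final visit.

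SAP 1.16 adds a fallback: if a logistic model does not converge, nothing is imputed, and the Newcombe interval and Barnard's test are used.

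**The concern.** Multiple imputation here assumes that, given arm and earlier VMT status, loss is unrelated to the 24-week outcome. Complete-case also ignores any dependence of loss on that outcome. Setting one beside the other therefore leaves the doubtful assumption untested.

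Three features of the plan add to this.

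- An imputed eye has, by definition, no earlier release, so every VMT status observed for it is unreleased. With ERM removed, imputation rests on arm and on which visits were attended.
- Complete-case keeps lost eyes that had released and drops lost eyes that had not, so it can overstate release in each arm.
- Under the SAP 1.16 fallback nothing is imputed. The primary and sensitivity analyses then use the same eyes and coincide.

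Informative loss is plausible, though not shown. Protocol 1.5 expects PVL participants to be likely to see the bubble, and investigators and coordinators are unmasked. The SAP version table reports a smaller than anticipated sample after early stopping for safety concerns, so each unresolved eye carries more weight. At stake is whether readers can tell a robust primary result from a fragile one.

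**Working it through.** **Inputs.** Protocol 8.3.2 gives "error rate of 5%, 90% power, and a two-sided test of superiority", then "For true outcome proportion of 60% (PVL) vs 30% (sham injection), a sample size of 112 (56" per group), and "loss to follow-up of 10% gives a final sample size of 124 (62 per group"). Allocation is equal (Protocol 2.4). SAP 1.12 treats P ≤ .05 as of interest.

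**The plan's own figure.** With pooled variance and no continuity correction, n per arm = [1.960 √(2 × .45 × .55) + 1.282 √(.6 × .4 + .3 × .7)]² / .30² = 55.7, so 56 per arm and 112 in total, as stated. For loss, 112 × 1.1 = 123.2 and 112 / 0.9 = 124.4; the stated 124 is close to both. The allowance is 62 − 56 = 6 lost eyes per arm.

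**Method.** SAP version 2.0 has no covariate in the primary model, so a two-by-two comparison is a close stand-in for it. z = (p1 − p2) / √[p̄(1 − p̄)(1/n1 + 1/n2)], with p̄ the pooled proportion. Barnard's test is shown as well, because it is the SAP 1.16 fallback. All scenarios take about 10% lost per arm, with every lost eye unresolved. In the last column, unresolved PVL eyes are failures and the stated number of unresolved sham eyes are releases. P values in the table are Barnard's unless marked.

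| Scenario | Complete-case | All unresolved eyes failures | Adverse combination |
|---|---|---|---|
| 62 per arm, 6 unresolved each, 60% v 30% | 34/56 v 17/56, 30.4 points, P = .0014 | 34/62 v 17/62, 27.4 points, P = .0020 | all 6 sham release: 34/62 v 23/62, 17.7 points, z P = .047, Barnard P = .053 |
| 62 per arm, 6 each, 50% v 30% | 28/56 v 17/56, 19.6 points, P = .037 | 28/62 v 17/62, 17.7 points, P = .042 | 1 sham release: 28/62 v 18/62, 16.1 points, P = .067 |
| 30 per arm (assumed), 3 each, 60% v 30% | 16/27 v 8/27, 29.6 points, P = .033 | 16/30 v 8/30, 26.7 points, P = .039 | 1 sham release: 16/30 v 9/30, 23.3 points, P = .075 |
| 40 per arm (assumed), 4 each, 70% v 20% | 25/36 v 7/36, 50.0 points, P < .0001 | 25/40 v 7/40, 45.0 points, P < .0001 | all 4 sham release: 25/40 v 11/40, 35.0 points, P = .0018 |
| 20 per arm (assumed), 2 each, 70% v 20% | 13/18 v 4/18, 50.0 points, P = .0039 | 13/20 v 4/20, 45.0 points, P = .0046 | both sham release: 13/20 v 6/20, 35.0 points, P = .034 |

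First-row worst case in full: p̄ = 57/124 = .460; SE = √(.460 × .540 × 2/62) = .0895; z = .1774/.0895 = 1.98; P = .047. The Wald 95% CI is 0.5 to 35.0 points.

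**Fewer unresolved eyes.** The 10% is total loss. In the one PVL series with two time points (Protocol 1.1.3), release was 40% at one month and 60% by six months, so about half of 6 lost PVL eyes might already count as released. Assume 3 unresolved PVL and 5 unresolved sham eyes, with the same release rates among resolved eyes: 59 × 34/56 = 35.8 and 57 × 17/56 = 17.3, rounded to 36 and 17. The worst case is then 36/62 v (17 + 5)/62 = 22/62, 22.6 points, z P = .012, Barnard P = .013.

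**The case against.** The strongest case against is that the gap is narrow and the result at the planned size is safe. The early-release and rescue rules settle many lost eyes, the week-24 analysis window of 126 to 280 days (SAP 1.13) captures late visits, and the Coordinating Center tracks participants whom sites cannot reach (Protocol 7.2). The worst case at the design effect needs all 12 lost eyes to be unresolved and to go the wrong way, and on the z test it still meets P ≤ .05. The scenarios that tip start near .05 or use a trial size that the documents do not give. A reader could also build the worst-case table from the reported proportions and visit completion, if denominators are shown. All of this stands, and it limits the size of the point.

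Two stronger readings are tempting, and the documents do not support them.

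- A reader might infer that complete-case must agree with the imputed result. It need not: complete-case removes only eyes not yet released, and imputation puts them back, so the comparison carries some information, only not about informative loss.
- A reader might infer that a lost PVL eye operated on elsewhere is imputed at the overall PVL release rate. Imputation conditions on earlier VMT status, so an eye seen unreleased is imputed from similar unreleased eyes. The inference fits only an eye with no follow-up OCT. If the outside surgery becomes known as rescue before 24 weeks, the eye is a failure by rule.

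The objection does not supply an analysis in the plan that lets loss depend on the unseen outcome.

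**Conclusion.** The point holds as a gap in the sensitivity analysis; the primary analysis itself is not in error. The plan offers one check on missing primary outcomes, and that check cannot detect loss related to the unobserved outcome; under the non-convergence fallback it is no separate check at all.

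The consequence depends on two numbers that the documents do not give, the final sample size and the count of unresolved eyes. At the planned size and effect the result is fairly robust, and a reader should not infer that a few lost eyes would overturn it. With an observed 50% v 30%, or an assumed 30 per arm at 60% v 30%, one lost sham eye releasing while the lost PVL eyes fail carries P past .05. At 70% v 20% with the assumed 20 or 40 per arm, even the worst case stays below .05. The planned analyses cannot separate these situations. The illustrations rest on about 10% loss per arm with every lost eye unresolved, which is an upper bound at that loss rate.

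**What to change.** In SAP 1.4, add a tipping-point table. Over every combination of the number of unresolved eyes counted as released in each arm, from none to all, give the risk difference, its confidence interval and the P value. Mark the missing-equals-failure and worst-case cells, and state the least extreme combination that changes the conclusion. Report the number of unresolved eyes per arm beside it. Keep complete-case as a secondary check and leave the primary analysis as it is.

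Label the table post hoc, because SAP version 2.0 was itself revised after review of study data.

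The cost is a few lines of SAP text and one small deterministic table, with no new data. The downside is that the result may look less certain; if few eyes are unresolved, the table will simply show that the result is robust.
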